Rationale for change	Requirements were adjusted to allow the PK assessment in both q.d. and b.i.d. dosing schedule.
Section to be changed	
Description of change	
Rationale for change	
Section to be changed	7.1 STATISTICAL DESIGN – MODEL
Description of change	Descriptions of BI 891065 doses in section 7.1 tables were updated to clarify whether they are q.d. or b.i.d.
Rationale for change	Clarification
Section to be changed	7.1.1 Part A
Description of change	
Added:
 
The BLRM is set up for a fixed dosing schedule of once daily (q.d.) across dose levels of BI 891065. For the purpose of dose-toxicity modelling, a b.i.d. regimen will be converted in the BLRM to an equivalent q.d. regimen that has a similar Cmax at steady state, based on the assumption that safety events are triggered by Cmax at steady state. For example, the 200 mg b.i.d. regimen will be modelled as equivalent to a 300 mg q.d regimen in reference to the simulation results from trial 1379-0001. For any other b.i.d. doses considered, their conversions will be specified in the TSAP. If multiple b.i.d. doses are tested, appropriate modifications to the BLRM to account for the heterogeneity of different dosing schedules might be considered.
 
Details will be specified in the TSAP if needed.

Rationale for change	Methods of using BLRM in b.i.d. dosing were clarified.
Section to be changed	7.1.2 Part B
Description of change	
The BLRM is set up for a fixed dosing schedule of once daily (q.d.) across dose levels of BI 891065. For the purpose of dose-toxicity modelling, a b.i.d. regimen will be converted in the BLRM to an equivalent q.d. regimen that has a similar Cmax at steady state, based on the assumption that safety events are triggered by Cmax at steady state. For example, the 200 mg b.i.d. regimen will be modelled as equivalent to a 300 mg q.d regimen in reference to the simulation results from trial 1379-0001. For any other b.i.d. doses considered, their conversions will be specified in the TSAP. If multiple b.i.d. doses are tested, appropriate modifications to the BLRM to account for the heterogeneity of different dosing schedules might be considered.
 
Details will be specified in the TSAP if needed.

Rationale for change

Methods of using BLRM in b.i.d. dosing were clarified.

11.4 GLOBAL AMENDMENT 4

Date of amendment	30 Apr 2021
EudraCT number	Not applicable
EU number	
BI Trial number	1379-0006
BI Investigational Medicinal Product(s)	BI 891065 BI 754091
Title of protocol	An open label, Phase I study of BI 891065 monotherapy and combination therapy of BI 891065 and BI 754091 in Asian patients with advanced solid tumours
Global Amendment due to urgent safety reasons	
Global Amendment	
Section to be changed	Flowchart footnote and sections 6.2.3.5 and 10.3.
Description of change	Descriptions to reduce the required study procedures and data collections were added.
Rationale for change	The assessments of primary and secondary endpoints have been completed, and sufficient data have been collected for further endpoint by an interim DBL on 29 Mar 2021. The CTR will be prepared based on the data locked at this interim DBL. As of April 2021, one patient is still receiving the study treatment as per the protocol, but further data collection is no longer needed for the analysis. Therefore, the data to be collected will be reduced to a necessary minimum. The assessments will be performed as medically indicated to monitor the safety at the discretion of the investigator, and the results will be documented in the source data but will not be collected in the eCRF except for AE/SAE and the information about the treatment continuation and study termination.
Section to be changed	Section 5.4.4
Description of change	A statement was added that the genotyping analysis was cancelled.
Rationale for change	Based on the clinical outcome, the sponsor concluded that the genotyping analysis would not result in gaining additional supportive information.

APPROVAL / SIGNATURE PAGE

Document Number: c27190653

Technical Version Number: 5.0

Document Name: clinical-trial-protocol-version-05

Title: An open label, Phase I study of BI 891065 monotherapy and combination therapy of BI 891065 and BI 754091 in Asian patients with advanced solid tumours

Signatures (obtained electronically)

Meaning of Signature	Signed by	Date Signed
Author-Clinical Trial Leader	 A large black rectangular redaction box covering the signature area.	07 May 2021 03:51 CEST
Author-Trial Clinical Pharmacokineticist	 A large black rectangular redaction box covering the signature area.	07 May 2021 07:01 CEST
Approval-Team Member Medicine	 A large black rectangular redaction box covering the signature area.	07 May 2021 08:31 CEST
Approval-Therapeutic Area	 A large black rectangular redaction box covering the signature area.	07 May 2021 14:27 CEST

2. LIST OF ABBREVIATIONS

| Term | Definition / description |
|---------|---|
| ADA | Anti-drug Antibody |
| AE | Adverse Event |
| AESI | Adverse Event of Special Interest |
| AGP | Alpha-1 Acid Glycoprotein |
| ALT | Alanine Aminotransferase |
| ANC | Absolute Neutrophil Count |
| aPTT | Activated Partial Thromboplastin Time |
| ATC | Anatomical Therapeutic Chemical |
| BI | Boehringer Ingelheim |
| BLRM | Bayesian Logistic Regression Model |
| BMI | Body Mass Index |
| cIAP | Cellular Inhibitor of Apoptosis |
| CR | Complete Response |
| CT | Concomitant Therapy |
| CTCAE | Common Terminology Criteria for Adverse Events |
| CTP | Clinical Trial Protocol |
| CTR | Clinical Trial Report |
| DILI | Drug-induced Liver Injury |
| DLT | Dose-limiting Toxicity |
| ECG | Electrocardiogram |
| ECGPCS | Electrocardiogram Pharmacokinetic Concentration Set |
| ECOG | Eastern Cooperative Oncology Group |
| eCRF | Electronic Case Report Form |
| ES | Enrolled Set |
| HR | Heart Rate |
| ICH | International Conference on Harmonization |
| iCPD | Immune Confirmed Progressive Disease |
| iCR | Immune Complete Response |
| iPR | Immune Partial Response |
| IPD | Important Protocol Deviations |
| iRECIST | modified RECIST 1.1 for immune-based therapeutics |

| | |
|-------------|---|
| iSD | Immune Stable Disease |
| iUPD | Immune Unconfirmed Progressive Disease |
| MedDRA | Medical Dictionary for Regulatory Activities |
| msec | milliseconds |
| MTD | Maximum Tolerated Dose |
| NSCLC | Non-small Cell Lung Cancer |
| OR | Objective Response |
| ORR | Objective Response Rate |
| PBMCs | Peripheral Blood Mononuclear cells |
| PD | Progressive Disease |
| PK | Pharmacokinetics |
| PKS | Pharmacokinetic Set |
| PR | Partial Response |
| PR interval | ECG interval from the onset of the P wave to the beginning of the QRS complex |
| PT | Preferred Term |
| QRS | Combination of the Q, R and S waves |
| QT | ECG interval from the beginning of the QRS complex to the end of the T wave |
| QTc | Generic term for QTcF and QTcB intervals |
| QTcB | QT interval, corrected by Bazett's formula |
| QTcF | QT interval, corrected by Fridericia's formula |
| RECIST | Response Evaluation Criteria In Solid Tumours |
| REP | Residual Effect Period |
| SCR | Screened Set |
| SD | Stable Disease |
| SMAC | Second Mitochondrial Activator of Caspases |
| SMC | Safety Monitoring Committee |
| SOC | System Organ Class |
| StD | Standard Deviation |
| TS | Treated Set |
| TSAP | Trial Statistical Analysis Plan |
| ULN | Upper Limit of Normal |
| WHO DD | World Health Organisation Drug Dictionary |

4. CHANGES IN THE PLANNED ANALYSIS OF THE STUDY

All analyses described in the CTP will be carried out.

5. ENDPOINTS(S)

5.1 PRIMARY ENDPOINT(S)

Part A:

The primary endpoints for Part A of the trial are:

- Maximum tolerated dose (MTD)
- the number of patients with dose-limiting toxicities (DLTs) during the MTD evaluation period (first treatment cycle).

For definition of the MTD, refer to Section 2.1.1 of the CTP.

5.2 SECONDARY ENDPOINT(S)

5.2.1 Key secondary endpoint(s)

Not applicable.

5.2.2 Secondary endpoint(s)

Part A:

- The pharmacokinetics (PK) parameters of BI 891065 will be calculated in cycle 1: $C_{max(ss)}$, AUC_{0-24} and $AUC_{\tau,ss}$ of BI 891065

6. GENERAL ANALYSIS DEFINITIONS

6.1 TREATMENT(S)

In Part A of this Phase I trial, treatments are not randomized. Different dose levels and dose schedule of BI 891065 monotherapy are being administered.

The data will be presented only for Part A, because Part B was cancelled, as mentioned earlier.

For safety summaries events that start from the first administration of any trial medication until 30 days (REP) after the last administration of any trial medication will be considered as having occurred “on-treatment”. If not specified otherwise, all safety tables will be based on the on-treatment period. Adverse events that have onset during the screening or the follow-up period will be displayed in separate listings from those that occurred during the on-treatment period. The MTD evaluation period will be defined as the period from 1st treatment administration (day 1) till day 21 inclusively.

Labels of each treatment period, the labels used for displays in the tables and listings in the CTR, as well codes, decodes, sort order and labels for each trial medication are provided in the TSAP technical documents.

6.2 IMPORTANT PROTOCOL DEVIATIONS

Important protocol deviations will be summarised. The IQRMP specifies the important protocol deviations in detail. The following table specifies the different categories of IPDs.

Table 6.2: 1 Handling of iPDS

| iPD code | | iPD Category & Brief Description | Excluded from analysis set |
|-----------------|----|---|-----------------------------------|
| A | | In/Exclusion criteria not met | None |
| | A1 | Inclusion criteria not met | None |
| | A2 | Exclusion criteria not met | None |
| B | | Informed consent not available/not done | |
| | B1 | Informed consent not available/not done | All |
| | B2 | Informed consent too late | None |
| C | | Trial medication and randomization violations | |
| | C1 | Incorrect trial medication taken | None |
| | C2 | Administration not according to protocol | None |
| | C3 | Administration of study medication which exceeded the limit of in-use stability | None |
| D | | Prohibited medication use | |
| | D1 | Concomitant medication | None |
| E | | Missing critical data | |
| | E1 | Missing of Vital signs (BP, PR, BT and SpO2) | None |
| | E2 | Missing of 12-Lead ECG | None |
| | E3 | Missing of Safety laboratory parameters | None |
| | E4 | Important AE related data missing | None |

6.3 SUBJECT SETS ANALYSED

The Screened Set (SCR) includes all patients who signed the informed consent form and will be used to summarise patient disposition.

The Enrolled Set (ES) includes all patients who have been enrolled into the study.

The Treated Set (TS) consists of all patients who have received at least one administration of trial medication and will be used for all planned safety, efficacy and biomarker analyses in the CTR besides the MTD determination.

The MTD Evaluation Set includes all patients who were documented to have received at least one dose of trial medication and were considered evaluable for MTD evaluation. This set will be used for the primary analyses of DLTs and MTD determination.

Rules for replacement of patients are defined in CTP Section 3.3.4.1. The list of replaced patients will be stored in the trial master file.

The Pharmacokinetic Parameter Set (PKS) consists of all patients in the TS who have at least one PK endpoint that was not excluded due to a protocol deviation relevant to the evaluation of PK or due to PK non-evaluability.

The ECG Set includes all patients in the treated set who do not have an artificial pacemaker and have at least one on-treatment value for at least one ECG variable.

6.5 POOLING OF CENTRES

This section is not applicable since there will be no inferential analyses. Thus, no statistical model in which centre or country is included as factor will be applied.

6.6 HANDLING OF MISSING DATA AND OUTLIERS

Missing or incomplete AE dates are imputed according to BI standards (4). Missing data and outliers of PK data are also handled according to BI standards (5). PK parameters that cannot be reasonably calculated based on the available drug concentration-time data will not be imputed. Potential outliers will be reported and analysed as observed. In general, missing data not discussed in (4) and (5) will not be imputed unless required for the following analyses and definitions. Then the rules as described below apply.

1) Change of laboratory values from baseline

Laboratory values at baseline: For missing laboratory data at cycle 1 day 1 (before the first administration of any study medication) the data of preceding visits will be used if available.

2) Definition of on-treatment period and actual treatment

Date of permanent discontinuation of study medication: All reasonable efforts should be undertaken during the study to obtain the dates of permanent discontinuation of study medication. However, if the date of the very last administration is missing this will be imputed with:

- If only month and year are given, the last day of the month will be used for imputation

- If only the year is given, the 31st of December of the given year will be used for imputation

If the imputed date leads to a date that is later than the date of the EOT visit, then the imputed date is the date of the EOT visit. If the imputed date leads to a date that is later than the death date, then the imputed date is the date of death.

3) ECG analysis

Quantitative and derived categorical ECG endpoints

- If single cardiac cycles are missing, the arithmetic means per single ECG will be computed with the reduced (1, 2 or 3) number of cardiac cycles.
- If replicate ECG recordings are missing, the arithmetic means per time point will be computed with the reduced (1 or 2) number of recordings.
- If the actual times of all triplicate pre-dose ECG recordings on Day 1 or the time of the first drug administration are missing, or the planned pre-dose ECGs are recorded after the first drug administration, they will not be used as baseline values and will be excluded from the analyses.
- If baseline is missing, a QTcF/QT interval > 500 msec at any time on treatment will be a notable finding.

Qualitative ECG findings

- In case a certain qualitative ECG finding is not reported at baseline but occurring on-treatment, this will be categorized as a 'new onset' of this finding.
- For the analysis of overall ECG interpretation values (comparison of on-treatment with baseline results), missing values will be handled as indicated in the following table.

Table 6.6: 1 Interpretation of qualitative ECG findings

| Condition: Overall ECG interpretation | | Aggregated result presented in Table |
|--|---|---|
| At baseline | On treatment (specific time interval under consideration) | Overall ECG interpretation |
| Normal, abnormal or missing/not evaluable | Normal (all time points) | Normal |
| Abnormal | Abnormal (at least one time point) | Abnormal, and abnormal at baseline |
| Normal or missing/not evaluable | Abnormal (at least one time point) | Abnormal (new onset) |
| Normal, abnormal or missing/ not evaluable | Missing/not evaluable (at least one time point), normal or missing/not evaluable at the other time points | Missing/not evaluable |

Exposure-response analysis

- Missing BI 891065 plasma concentration data which are identified by “BLQ” in the comment field (below lower limit of quantification) will be replaced by $\frac{1}{2}$ LLOQ (lower limit of quantification) if measured on-treatment.

4) Biomarker and pharmacodynamic analysis

Cytokines: For cytokines, we impute BLQ values with $\frac{1}{2}$ LLOQ .

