6.7 BASELINE, TIME WINDOWS AND CALCULATED VISITS

Study days and visits will be labelled according to the flowchart in the CTP.

Unless otherwise specified baseline is defined as the time point closest to but prior to the first administration of study medication. If no time is specified and the date is the same as the first administration date, then it will still be considered baseline if not specified otherwise. If there

is no measurement earlier than the first administration of study medication, then no baseline will be derived.

Laboratory values:

Baseline is defined as the latest time point before the very first administration of study medication. For laboratories where not only the examination date but also time are recorded, examination time has to be taken into account when defining baseline. That is, a laboratory value on the same date as the first administration of study medication is considered as baseline value only if the time of laboratory assessment is before or the same as the time of first study drug administration.

If any of these times is missing and the date of laboratory assessment is equal to the date of first administration of study medication, then the laboratory assessment will be considered as according to protocol, i.e. as prior to first study medication.

Imaging time windows:

In order to identify whether consecutive imaging time points are missing for a given patient, a nominal time point (6, 12, ... weeks etc.) will be assigned to each and every image. This is achieved by creating windows for every radiological response assessment. These windows are defined in Table 6.7: 1.

Table 6.7: 1 Nominal time points and windows for imaging

| Nominal time point (weeks from start of study medication) | Planned date of scans (relative day*) | Window (days) |
|--|--|----------------------|
| 6 | 43 | 1 to \leq 64 |
| 12 | 85 | 65 to \leq 106 |
| 18 | 127 | 107 to \leq 148 |
| 24 | 169 | 149 to \leq 200 |
| 33 | 232 | 201 to \leq 263 |
| 42 | 295 | 264 to \leq 326 |
| 51 | 358 | 327 to \leq 389 |
| Etc., 9 week interval | Etc. | Etc. |

* the date of the first dose of study medication is Day 1

If a patient does not have an image in one of the windows described above, he/she will be said to have missed an assessment for that time point.

ECG analysis:

Baseline values will be derived from the 1–3 triplicate ECG recordings prior to the first drug administration on Day 1 (refer to [Section 7.8.4](#)).

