7.8.2 Laboratory data

The analysis of laboratory data will be descriptive in nature and will be based on BI standards (7). The same on-treatment period as considered for the analysis of adverse events will be applied for laboratory values. Patients having at least one post-baseline laboratory value will be displayed in the descriptive analyses. Patients with missing CTCAE grade at baseline or no baseline value but with post-baseline values will be displayed in a new category “missing CTCAE grade at baseline” for those laboratory parameters where CTCAE grading is applicable. Descriptive statistics, including change from baseline and frequency of patients with transitions relative to the reference range, will be provided. CTCAE grades for applicable laboratory parameters will be calculated according to CTCAE v5.0.

For Primary laboratory tests listed in Table [7.8.2: 1](#), the following outputs will be presented:

- Descriptive statistics, including changes from baseline
- Shift tables in terms of:
 - CTCAE grade, for laboratory tests with CTCAE grade defined;
 - Upper and lower reference limits, for laboratory tests without CTCAE grades;
 - Multiples of upper reference limit for customized shift tables of ALP, ALT, AST, total bilirubin and creatinine.
- Frequency of patients with potential clinically significant abnormalities.

For secondary laboratory tests listed in Table [7.8.2: 2](#), analyses will be limited to frequency of patients with potential clinically significant abnormalities.

For other laboratory tests, only listing of observed values will be presented.

Analyse of descriptive statistics should use normalized lab values. Analyses of frequencies of patients with potential clinical significance, analyses of shift, and liver function categories tables should use converted values.

Table 7.8.2: 1 Primary laboratory tests

Table 7.8.2: 2 Secondary laboratory tests

| Label | Lab test name | Direction of interest | Potential Clinical significance rule |
|-------|----------------------------|-----------------------|---|
| ALB | Albumin | Low | A ¹ |
| APTT | Activated Prothrombin Time | High | A ^{1,2} |
| CA | Calcium | Low, High | A ¹ |
| CL | Chloride | Low, High | Low: <80 mmol/L and <baseline High: >120 mmol/L and >baseline No CTCAE defined |
| EOS | Eosinophils | High | >1.0*10 ⁹ /L and > baseline No CTCAE defined |
| GGT | Gamma Glutamyl transferase | High | CTCAE Grade 2 or higher |

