Frequency tables will be provided for all categorical variables including notable findings and qualitative ECG findings. The tables will be presented separately for the visit days where an ECG profile has been taken as well as for the overall on-treatment period using the maximum value per patient. Frequencies of the increases in QTcF and QT intervals above thresholds as defined in [Section 5.4.3](#) between baseline and on-treatment will be displayed in two-way shift tables by treatment. Frequency tables with regard to the new onset of qualitative (morphological) ECG findings will display categories of grouped findings based on the CDISC (EGTEST) terminology as well as the frequencies per each observed type of finding. These descriptive analyses will be performed for patients in the ECG Set for Part A.

For all patients with any notable finding (see [Section 5.4.3](#)), a separate listing in Section 15 of the CTR will be created and the corresponding time profiles will be shown. Notable findings of patients in the TS who are excluded from the ECG Set will be listed in separate listings.

Exposure-response analysis

All exposure-response analyses will be based on the ECGPCS. The decision whether plasma concentration values, which are excluded from the descriptive PK analyses, are to be excluded from the exposure-response analysis as well, is to be made no later than at the RPM before data base lock. Pairs of BI 891065 plasma concentrations and QTcF changes from baseline that are not time-matched (i.e. an unacceptable time deviation between PK blood sampling and ECG recording) will be excluded from the analysis. The maximum time deviation between PK blood sampling and ECG recording at different time points during the trial that will be accepted for the analysis are listed in Table 7.8.4: 1. For pre-dose pairs, both measurements had to be collected before the corresponding drug administration; for post-

dose pairs, both measurements had to be collected after the corresponding drug administration. In case the collecting time of the PK blood sample and/or the ECG recording is not available, the pair will also be excluded from the analysis.

Table 7.8.4: 1 Maximum acceptable time deviations between PK sample and ECG recording

| Timepoint of ECG recording* | Acceptable deviation | Timepoint of ECG recording* | Acceptable deviation |
|-----------------------------|----------------------|-----------------------------|----------------------|

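### Two ECG rules in SAP 6.6 can misclassify a patient: mistimed pre-dose ECGs drop out of the on-treatment tables, and a missing baseline is reported as 'new onset'

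*SAP*

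**What the plan says.** **Mistimed pre-dose ECGs.** Under the SAP 6.6 subheading for quantitative and derived categorical ECG endpoints, planned pre-dose ECGs on Day 1 "recorded after the first drug administration, they will not be used as baseline values and will be excluded from the analyses". The same consequence follows if the times of all pre-dose triplicates, or the time of the first dose, are missing. The next bullet reads: "If baseline is missing, a QTcF/QT interval > 500 msec at any time on treatment will be a notable finding".

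**Missing baseline, qualitative findings.** Under a separate subheading, a "qualitative ECG finding is not reported at baseline but occurring on-treatment, this will be categorized as a 'new onset" of that finding. For the overall interpretation, row 3 of Table 6.6: 1 reads "Normal or missing/not evaluable | Abnormal (at least one time point) | Abnormal (new onset" (baseline, on treatment, reported result).

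**How the results are used.** SAP 6.7 defines baseline: "Baseline values will be derived from the 1–3 triplicate ECG recordings prior to the first drug administration on Day 1". SAP 6.1 counts the on-treatment period from the first administration of trial medication and bases safety tables on it unless stated otherwise. SAP 7.8.4 tabulates notable and qualitative findings by ECG visit day and for the "overall on-treatment period using the maximum value per patient". It also tabulates new onset of qualitative findings as a frequency.

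**Laboratory data, for contrast.** In SAP 7.8.2, patients with a missing baseline CTCAE grade or "no baseline value but with post-baseline values will be displayed in a new category" of their own.

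**The concern.** Leaving a post-dose recording out of baseline and leaving it out of the on-treatment results are separate decisions. The first protects the change-from-baseline values. The second discards an observation made after exposure, and the SAP gives no reason for it. The two neighbouring bullets also pull apart: one looks for a long QTcF or QT at any time on treatment, while the other removes recordings that were made on treatment.

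Row 3 of Table 6.6: 1 merges two states of knowledge. With a normal baseline, an abnormal on-treatment ECG is new. Without a baseline, nobody can say whether it is new. The table has a missing category for the on-treatment side (row 4) but none for the baseline side.

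The stake is the descriptive ECG safety result. It consists of counts in very small dose cohorts, so one patient in the wrong cell is visible.

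**Working it through.** The documents give no figure for this point, so there is none to reproduce. The check is a reading of the rules followed by a scale for one patient.

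**Step 1: mistimed recording.** Take a patient in a cohort of 3 whose three planned pre-dose triplicates (1 h, 30 min and 15 min before dosing, Protocol Table 10.3: 1) were all recorded after the first dose, with times known.
- There is no ECG baseline (SAP 6.6 and 6.7), so the absolute 500 msec rule applies.
- Suppose QTcF exceeds 500 msec on one of these recordings and nowhere else.
- SAP Table 7.8.4: 1 lists nine other Part A on-treatment time points: 1, 2, 3 and 24 h after the first dose; Day 15 pre-dose and 1, 2 and 3 h; Day 16 pre-dose. None shows the finding.
- As written, the table shows 0 of 3 patients. With the recording kept, it shows 1 of 3.
- If any of the nine also exceeds 500 msec, both versions show 1 of 3, and the rule does no harm to this count.

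**Step 2: row 3.** Classify patients with at least one abnormal on-treatment ECG:

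| Baseline | SAP label | What the data support |
|---|---|---|
| Abnormal | Abnormal, also at baseline | Same |
| Normal | New onset | Same |
| Missing or not evaluable | New onset | Abnormal, newness unknown |

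The total abnormal on treatment is the sum of the three lines and does not depend on the label. Only the new-onset count can change, and only upwards from the truth: it is overstated when the abnormality was already there before dosing.

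**Step 3: weight of one patient.** Protocol 3.1 sets at least 3 patients per cohort. The MTD rule in Protocol 7.1.1 asks for at least 6 at the MTD. Protocol 7.6 expects about 12 in Part A.
- 1/3 = 33 percentage points
- 1/6 = 17 points
- 1/12 = 8 points

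**Step 4: how often row 3 could matter.** Let q be the probability that a patient has no usable ECG baseline and a the prevalence of a pre-existing abnormality. Both are assumptions; the documents give neither. With n = 12, the chance of at least one patient without a baseline is 1 − (1 − q)^12, and the expected number of false new onsets is 12 × q × a.

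| q (assumed) | Chance of at least one patient without baseline | Expected false new onsets, a = 10% to 50% (assumed) |
|---|---|---|
| 1% | 11.4% | 0.012 to 0.06 |
| 5% | 46.0% | 0.06 to 0.30 |
| 10% | 71.8% | 0.12 to 0.60 |

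Over this range, fewer than one false new onset is expected in the whole of Part A.

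**The case against.** The best defence is that the trigger is remote and safety does not rest on these tables.
- Baseline survives if one of three triplicates is usable. Day 1 is an intensive PK day on which dosing times must be recorded (Protocol 5.3.1 and 5.3.2).
- Investigators read the ECGs themselves, base treatment decisions on their own reading and report clinically relevant abnormalities (Protocol 5.2.4).
- Individual ECG data are listed (SAP 7.8.4), and the analysis is descriptive.
- A mistimed recording has no slot in a summary by time point.
- Calling an unverifiable abnormality new is a pre-specified convention that leans towards showing a signal.

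Most of this stands and keeps the point small. Three parts do not fully answer it. Protocol 5.2.4 says that centrally detected abnormalities do not automatically qualify as AEs, so AE reporting is not a complete substitute. The lack of a slot is a reason to leave the recording out of the by-time-point summaries, but not out of the maximum. The cautious-convention argument covers row 3 only, since the exclusion rule leans the other way.

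A reader might also infer more than the text supports:
- *The two rules compound, so that an abnormality on a discarded pre-dose ECG comes back as new onset.* The exclusion stands under the quantitative subheading. Whether it also removes the qualitative baseline, or morphological findings on the recording, is not stated.
- *Any abnormality without a baseline becomes new onset.* That holds for qualitative findings and overall interpretation. QTcF and QT follow the absolute 500 msec rule.
- *ECG should follow the laboratory rule for a missing clock time,* under which "then the laboratory assessment will be considered as according to protocol, i.e. as prior to first study medication". The SAP 6.7 default yields where something else is specified, and for ECG it is. Admitting ECGs of unverified timing could put a post-dose value into the baseline behind every change from baseline and the exposure-response plots. That is a trade-off, not an error.

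**Conclusion.** The point holds in limited form. Each rule can put a patient in the wrong cell of a descriptive ECG table. The exclusion rule can hide a QTcF or QT above 500 msec, but only if the finding appears on the mistimed recording and on no other on-treatment ECG. Row 3 can overstate new onset.

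It would go too far to say that the on-treatment ECG counts are wrong in both directions. The documents show that they can be wrong for an occasional patient, and row 3 never alters how many patients are abnormal on treatment.

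Probably no patient or one is affected. That is a judgement, because the documents give no rate of mistimed or missing baselines. The primary endpoint is untouched: the MTD rests on DLTs. One reservation remains: SAP 5.4.3, which defines the ECG variables and notable findings, is not visible, so a further rule there cannot be excluded.

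**What to change.** Amend SAP 6.6 in two places.

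(a) Planned pre-dose ECGs with a confirmed time after the first dose are not used as baseline and do not enter the by-time-point summaries. They are kept as on-treatment values for the maximum QTcF/QT and for notable findings. The exclusion stays for recordings whose timing cannot be verified.

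(b) Split row 3 of Table 6.6: 1. 'Abnormal (new onset)' then requires a normal baseline, and 'Abnormal (baseline missing/not evaluable)' becomes a category of its own. Word the first qualitative bullet the same way, so that a finding counts as new only against an evaluable baseline that did not show it.

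The cost is a few lines of SAP text, one extra table category and minor programming. No new data are needed.
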